Appendix 2 Protocol for [name] Lab at Lakeshore Campus:

Nanosep Tube Preparation

Materials Required: Nanosep Tube, molecular grade Water, 70% Ethanol, 1% BSA in PBS, microcentrifuge

1. Pipet into the Nanosep Tube 500 μ L of 70% Ethanol and centrifuge the Column at 14,000g for 10 minutes
 - a. Discard the flow-through - May need to use a pipet to remove all of it
 - b. When centrifuging during any of these steps be sure not to over-centrifuge as this will cause the membrane to dry out
2. Pipet in 500 μ L of PCR Water and centrifuge at 14,000g for 7 minutes
 - a. Remove the flow-through - May need to use a pipet to remove all of it
3. Pipet in 500 μ L of Bovine Serum Albumin (BSA) and leave for at least an hour at room temperature
 - a. The BSA serves as the passivation step so that the membrane is not overly sticky and prevent the capture of non-phage materials
 - b. Do not centrifuge the BSA
 - c. This is a potential pause point if one cannot do the whole preparation in one day - Can be left overnight at room temperature
4. Pipet out BSA from the membrane
 - a. Be sure not to scratch the membrane when pipetting (can tilt to limit contact)
5. Wash the membrane with PCR Water
 - a. When washing use approximately 50 μ L of PCR water
 - b. Hold the column at an angle and dispense the water at the top of the membrane and remove at the bottom - Repeat until the water begins to appear cloudy
 - c. Be careful not to scratch the membrane
6. Add another 500 μ L of PCR Water to the Column and centrifuge at 14,000g for 5 minutes
 - a. Remove the flow-through - May need to use a pipet to remove all of it
7. If not using the column within 20 minutes, add 100 μ L of PCR Water to the Column and store at 4° C. Try to use refrigerated columns within 1 week.
 - a. This layer of water will prevent the membrane from drying out before use

Concentration Protocol

Materials Required: Prepared Nanosep Spin Column, urine sample, PBS, microcentrifuge

1. Add 1 mL of the Urine Sample to a microcentrifuge tube and centrifuge at 10,000g for 10 minutes
 - a. This will cause a pellet to form at the bottom of the tube - The pellet includes the bacteria and eukaryotic cells that were in the urine sample
2. Transfer the supernatant to a new microcentrifuge tube
 - a. Discard the tube with the pellet
3. Remove the 100 μ L of water from the membrane of the Nanosep Spin Column and add 500 μ L of the Urine sample supernatant to the membrane
4. Centrifuge the Nanosep Tube initially at 1,000g for 7 minutes
 - a. Continue to spin the Nanosep tube at 1,000g for decreasing amounts of time until approximately 50 μ L remain above the membrane
 - i. 50 μ L above the membrane appears almost as if there is no liquid left
 - ii. It is difficult to determine 50 μ L by eye so the use of a 50 μ L pipet is recommended in order to keep track of how much liquid is left above the membrane

- iii. If processing multiple samples at once, some will finish before others. Have additional tubes and sterile media available to prepare blanks for re-balancing the centrifuge.
 5. After the 50 μL have been collected, transfer it to a new microcentrifuge tube and add the remaining 500 μL of the Urine Sample Supernatant to the Nanosep Tube
 - a. Be sure to remove the flow-through
 6. Repeat Step 4 for the second volume of the Urine Sample Supernatant
 7. Discard the flow-through
- Optional Steps 8-10:
8. Add the 50 μL from the first round of spinning to the 50 μL from the second round of spinning in the Nanosep tube
 - a. After this step you should have approximately 100 μL of concentrated phage in the Nanosep tube
 9. Add 400 μL PBS to the 100 μL of concentrated phage
 10. Spin the PBS and phage at 1,000g for 5 minutes
 - a. Keep spinning at 1,000g for shorter amounts of time until approximately 50 μL of liquid remain above the membrane
 11. Add 1 mL of PBS to the pellet that was kept from Step 1 and spin at 10,000g for ten minutes
 12. Discard the supernatant and add the 50 μL from Step 10 to the pellet
 13. Use 20 μL of PBS to wash the Nanosep membrane
 - a. Use the same washing technique shown in Step 5 of the Nanosep Preparation
 14. After washing the membrane, add the 20 μL to the pellet

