Hypothesis (a): Women with T2DM who have less vitamin D will have will have a different FUM composition than those with sufficient vitamin D.

Hypothesis (b): Women with T2DM who have less vitamin D will have will have more LUTS than those with sufficient vitamin D.

Planned Analyses: For this secondary objective, a generalized linear mixed effects model will be used to determine the odds of at least one UTI as a function of ordinal vitamin D status (deficient, insufficient, and sufficient), again allowing random intercepts for each participant to account for within subject correlation due to repeated measurements; these models will specify a binomial distribution with logit link to determine the odds ratio for each pairwise comparison of vitamin D status. As before, extreme error variances will be monitored using the ratio of each model's Pearson chi-square fit statistic over its degrees of freedom. When necessary, a negative binomial link may be used to account for observed over-dispersion. Finally, a linear mixed effects model will be used to estimate the effect of ordinal vitamin D status on patients' FUM indices and microbial taxa count as well as their LUTS symptom severity score, again allowing random intercepts for each participant. For this objective, all model terms will be evaluated using an alpha level of 0.05 and the tests will be two tailed, meaning that an effect in either direction will be interpreted.

To compare vitamin D, LUTS and the FUM, each individual will function as her own control, with the first time point establishing the baseline FUM profile with which to compare the effect of treatment dose at 6 months (endpoint of trial). We will model the outcome using a GLMM, which takes into account the correlation between 2 observations on the same woman. We will determine if there is a change in a women's FUM baseline to end of study by treatment. We will use similar procedures to determine treatment group differences. Similar data analyses will be conducted on the urinary symptoms reported by each participant across time points and between groups.

Exploratory Aim: To examine the relationship of the phage activity with glycemic control, other labs including Urine PH in biobanked urine samples in the laboratory of [name].

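### In Appendix 2, the phage Concentration Protocol discards a pellet that Steps 11, 12 and 14 need, and Step 12 depends on an optional step

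*Combined protocol and SAP*

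**What the plan says.** The exploratory aim of the urinary microbiome sub-study (Section V.5.b, Data Analysis) is "To examine the relationship of the phage activity with glycemic control", other laboratory values and urine pH in banked urine. Section V.4 (Urinary Microbiome and Self-Report Measures) points to Appendix 2 for the working method of isolating phage. It is the only phage method in the document.

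In the Concentration Protocol of that appendix:

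- Step 1 spins 1 mL of urine. Its note says: "The pellet includes the bacteria and eukaryotic cells that were in the urine sample".
- Step 2 moves the supernatant to a new tube, and Step 2a says: "Discard the tube with the pellet".
- Steps 3 to 7 spin the supernatant through the membrane in two 500 µL loads. Each load is reduced to about 50 µL. The first 50 µL is moved to a separate tube; the second stays above the membrane.
- A label then reads "Optional Steps 8-10". Step 8 pools the two aliquots to about 100 µL, Step 9 adds 400 µL of PBS, and Step 10 spins down to about 50 µL.
- Step 11, outside that label, says: "Add 1 mL of PBS to the pellet that was kept from Step 1 and spin at 10,000g for ten minutes".
- Step 12 adds the 50 µL "from Step 10 to the pellet".
- Step 13 washes the membrane with 20 µL, and Step 14 adds that wash to the pellet.

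**The concern.** There are two separate conflicts. First, a technician working in numerical order has thrown the pellet away nine steps before it is called for, and that material cannot be recovered from the aliquot. No step says to keep it, and nothing makes Steps 11 to 14 an alternative to Step 2a.

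Second, the optional label covers only Steps 8 to 10, yet Step 12 consumes what Step 10 produces. A technician who skips the optional steps, as the text allows, holds two separate aliquots and has no instruction on which to use or whether to combine them.

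What is at stake is whether the phage measurement can be reproduced from the document. One laboratory could stop with a cell-free concentrate and another could recombine the concentrate with washed cells, both believing that they followed the appendix. Neither the appendix nor the exploratory aim sets a final volume, a target concentration or a correction back to the original urine volume. A difference in processing could therefore not be adjusted for afterwards.

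**Working it through.** The plan gives no concentration factor or sample size for this procedure, so there is no figure to reproduce. The check has two parts.

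**1. What each step needs, and whether it exists**

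| Step | Needs | Available if the text is followed in order? |
|---|---|---|
| 1 to 7 | urine, then supernatant | yes |
| 8 to 10 (optional) | both 50 µL aliquots | yes |
| 11 | pellet from Step 1 | no, discarded at Step 2a |
| 12 | pellet, and 50 µL from Step 10 | pellet: no; 50 µL: only if Steps 8 to 10 were done |
| 13 | membrane and PBS | yes |
| 14 | pellet, and the 20 µL wash | pellet: no |

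The failure is confined to Steps 11, 12 and 14. Skipping Steps 8 to 10 creates a further gap at Step 12 even if the pellet had been kept.

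**2. Nominal concentration under each route**

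Inputs, all from the Concentration Protocol: 1 mL = 1000 µL of urine; two aliquots of about 50 µL; about 50 µL after Step 10; 20 µL wash. Assumption: full phage recovery. Formula: fold-concentration = urine volume represented ÷ final volume.

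Before anything is added to a pellet:

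- Steps 8 to 10 done: 1000 / 50 = 20-fold.
- Steps 8 to 10 skipped, both aliquots combined: 1000 / (50 + 50) = 10-fold.
- Ratio: 20 / 10 = 2.0.

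After the 20 µL wash, supposing that a pellet had been kept and ignoring its own volume:

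- Steps 8 to 10 done: 1000 / (50 + 20) = 1000 / 70 = 14.3-fold.
- Steps 8 to 10 skipped, both aliquots combined: 1000 / (100 + 20) = 1000 / 120 = 8.3-fold.
- Ratio: 120 / 70 = 1.7.

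If only one aliquot went forward, it would represent 500 µL of urine: 500 / 70 = 7.1-fold after the wash.

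The 50 µL is approximate, and Step 4 itself says that it is hard to judge by eye. Let the residual be r µL at every stop. The ratio before the wash is 2r / r = 2 for any r. After the wash it is (2r + 20) / (r + 20): for an assumed r of 40 it is 100 / 60 = 1.67, and for an assumed r of 60 it is 140 / 80 = 1.75. A consistent misjudgement of the residual hardly moves the ratio, although unequal residuals between stops would.

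**The case against.** The strongest reply is that this is a bench-sheet matter. The method serves one exploratory aim of an added sub-study, with no hypothesis, named model, defined activity variable or sample size. The appendix is described as a working protocol, and one laboratory may well have a settled practice. All of this stands, and it sets the severity.

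Some stronger readings are tempting, but the documents do not support them:

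- *The procedure cannot be run at all.* Steps 1 to 10, which do the concentrating, can be run as written.
- *Losing the bacterial fraction harms the trial.* No analysis is shown to need the pellet of this aliquot. Bacterial data come from sequencing and culture (Section V.4), urine is collected in 60 mL cups, and consenting women may bank more (Section V.3). The loss is the pellet of 1 mL.
- *Half the phage is lost.* Step 5 keeps the first aliquot in its own tube. Its later use is unstated, but it is not thrown away.
- *Associations with glycaemic control or urine pH would be biased.* Nothing says that samples would be handled differently. Mixed handling would bias an association only if the choice tracked those variables; otherwise it adds noise.
- *The pellet was clearly meant to be kept.* Three later steps rely on it, which points that way. But Steps 11 to 14 could instead belong to the optional branch, since Step 12 uses the product of Step 10. The text does not settle it.

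The fold figures also need a caveat. The only written pooling is Step 8, so the combined-but-skipped route is hypothetical, and the after-wash figures presuppose a pellet that Step 2a removes.

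**Conclusion.** The point holds as an internal contradiction in a laboratory appendix. Steps 11, 12 and 14 cannot be completed by someone who has followed Step 2a, and Step 12 has no defined input when the permitted omission of Steps 8 to 10 is used. This is more than missing detail, because following the text in order irreversibly discards material that later steps require.

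The roughly 1.7- to 2-fold difference in nominal concentration would arise only if the optional steps were used for some samples and not others. It assumes full recovery and, where the steps are skipped, that both aliquots are combined. Because the activity assay is not defined, the effect of such a difference on the measured variable is unknown. The CES-D primary outcome, the secondary outcomes, the powered analyses and the sub-study's primary objectives are untouched. Severity is low.

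**What to change.** Before samples are processed, the laboratory should:

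1. Reconcile Step 2a with Steps 11 to 14. If Steps 11 to 14 are to be run, Step 2a must say to keep the pellet. If they are not, delete them or mark them as part of the optional branch.
2. Either make Steps 8 to 10 required, or omit them and state the pooled input to Step 12.
3. Apply that one version to every sample.
4. Record the final volume for each sample, so that phage results can be expressed per original mL of urine.

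The cost is a few wording edits and one recorded volume, with slightly more bench time per sample if Steps 8 to 10 become required. If any samples have already been processed, noting which route each one took would allow the difference to be described.
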